Instead, we propose to estimate the cost of usual care for the sham-rTMS group during the pre-intervention acute treatment phase using HERC estimates of all (inpatient and outpatient) VA health care costs during the 6-month period immediately preceding the date of study recruitment. Using these cost estimates, we will calculate each patient’s *average estimated daily health care cost*. We will multiply these estimated daily cost values by the average duration (in days) of the acute treatment phase, measured from first to last day of rTMS therapy, among patients randomized to active-rTMS. The average duration represents the expected number of days of usual care that essentially will be foregone as a result of receiving active-rTMS. The product of the average daily health care cost value and the average duration will be our imputed value for the usual cost of care in the sham-rTMS treatment group during the acute treatment phase of the trial.

Mortality. Mortality information is potentially significant to this economic study because of the potential for patients who die to have very high health care costs just prior to expiring. Deaths will be identified by searching the VA Patient Treatment File and the VA Beneficiary

Identification and Record Locator System (BIRLS) death file. In sensitivity analyses, all analytical findings will be replicated leaving patients who died during the treatment or follow-up periods out of the analytical sample. The resulting estimates will be compared with results from the complete sample and any differences will be noted in our reporting of the research findings.

Inflation and Discounting. Dollar amounts in the study will be presented in terms of the price level as of the last year of data collection. We will adjust costs for inflation using the Consumer Price Index (CPI) for all urban consumers and all goods, the most common measure of nationwide inflation. The CPI is calculated on the basis of a basket of 305 items representing all goods and services purchased for everyday living by all urban residents. We will follow standard discounting methods, and discount health benefits and expenditures at a rate of 3% per year.¹ As noted earlier, HERC cost estimates are adjusted for regional differences in health care labor costs.

Discussion of the Rationale for Exclusion of non-VA Costs. As we noted above, we have chosen to limit our economic focus to VA health care costs only. Clearly, we have the opportunity to also collect data on non-VA health care costs. We recognize that a substantial proportion of these CSP 556 study participants' health care utilization may occur outside the VHA system and that it is generally desirable to measure non-VA treatment and caregiver costs. However, we believe that the gain in knowledge that could result from an effort to measure non-VA health care costs does not justify the additional research cost that would be required to obtain usable information on non-VA costs. In particular, we expect that Medicaid reimbursements account for a substantial proportion of non-VA expenditures among treatment-resistant VA patients. To obtain access to Medicaid data we would need to overcome numerous administrative hurdles, including gaining permission from each state's Medicaid agency. This has become a lengthy and sometimes infeasible process since the implementation of HIPAA privacy regulations. Access to private insurance claims is also potentially problematic, and working with claims from numerous private insurance carriers is onerous and labor intensive. Medicare files are available for VA patients, but Medicare may cover only a handful of patients in this study.

Estimation of non-VA patient and caregiver indirect costs is also potentially problematic, and therefore may not be justifiable given the required added research costs. Information on caregiver costs and patients' indirect costs is potentially unreliable due to several factors, including stigma associated with psychiatric problems and disability, difficult relationships between patients and family members, and cognitive problems. Although it is possible to address these issues through careful study planning and thorough data verification steps, the

additional expense and the risk that the resulting data would be incomplete and/or unreliable suggest that such an enterprise may not be justified in the current study.

4. Cost-Effectiveness Analysis

The remission outcomes data – where a sustained remission is defined as HRSD \leq 10 at 6-weeks post-treatment – will be used in conjunction with incremental treatment cost estimates to determine an incremental cost-effectiveness ratio (ICER) for the intervention. The resulting ICER will represent the estimated incremental cost per sustained remission, measured at 6-weeks post-treatment. The ratio will be expressed as: $ICER = [E(C | T_a) - E(C | T_u)] / [P(R | T_a) - P(R | T_u)]$, the difference in average acute treatment costs divided by the difference in probability of remission (R) between the two groups. Note that this assumes that the P(R) among patients receiving sham-rTMS is approximately equal to the probability of remission among usual care patients. A 95% confidence region surrounding cost-effectiveness ratios will be estimated using bootstrapping methods.¹⁷⁻¹⁹

The cost-effectiveness analysis could produce one of three major results: (1) rTMS may be cost neutral or less expensive and also more effective than usual depression care, indicating that its implementation is highly desirable; (2) rTMS might not be shown clinically effective in the VA, in which case its relative cost impact is irrelevant to VA decision-makers; (3) rTMS therapy will be more expensive than sham but will yield a greater likelihood of sustained remission. In this last case, the costs of a sustained remission will be compared with the cost of the main alternative treatment option, namely ECT. Estimates of ECT costs will be derived from the literature and from VA administrative sources.⁴

5. Sensitivity Analyses

We will test the sensitivity of our results to a number of assumptions. At a minimum, we expect them to include:

Discount and Inflation Rates. Costs incurred in earlier years must be inflated over time to maintain a steady level of purchasing power. They must also be inflated over time to reflect the discount rate, the rate at which people value money today over the same amount of money next year. The inflation rate, which we will measure by changes in the Consumer Price Index (CPI), could be varied in two ways for a sensitivity analysis. One is to use an alternative inflation measure, such as changes in the Gross Domestic Product Implicit Price deflator. We will use the CPI for main analyses and the Gross Domestic Product Implicit Price Deflator in the sensitivity analysis. A second approach is to vary the CPI by a small percentage, such as +/- 1.0% per year. Likewise, we will vary the assumed 3% discount rate by using alternative rates, such as 2% or 5%.

Usual Cost of Care. We will test our assumption that our imputed average costs in usual care for patients randomized to sham-rTMS are typical of treatment-resistant patients with major depression by comparing our average costs estimates for this group to a similar group of VA patients who are not participating in CSP 556. We will use Austin OPC-file data patients who were screened for participation in the study to estimate a propensity score for treatment-resistance among patients with a major depression diagnosis. The propensity score predictors will include an algorithm for possible treatment-resistance, which will be based on ICD-9 codes, number of changes in antidepressant medications in the past 12 months, treatment with a mood stabilizer, receipt of ECT, and other factors identified in extant studies.^{6, 7, 9, 10} Using this propensity score metric, we will identify treatment-resistant likely patients in the VA, and estimate their average health care costs and the variance of costs. Statistics for mean and variance will be compared with analogous sample parameters for patients randomized to sham. Based on these comparisons, we will define sensitivity ranges and apply them to our cost-effectiveness and cost-consequences estimates.

6. Power Analysis.

We do not present power analysis data. The extant literature provides too little information to make such an analysis informative. A key purpose of the cost-consequences analyses is to establish potential bounds for cost-offset effects resulting from rTMS, which are a necessary component of a power analysis. Also, the clinical study is adequately powered to detect a difference in health outcomes. We believe that an important finding of the economic study will be set of bounds for the potential cost-offsets that are associated with a depression remission among treatment-resistant patients with major depression. Whether or not these estimates reach statistical significance at conventional levels, they will provide critical information about the potential cost-effectiveness of expanded investment in emerging therapeutic technologies for treatment-resistant patients. They will be useful both in conducting future economic evaluation studies using the VA's large administrative databases as well as in ensuring that future cost-effectiveness studies in depression treatment are adequately powered.

E. Administrative policy

Economics data will be managed in the same way as the clinical data. We will adopt the same procedures and policies developed in the clinical study.

F. Project Coordination and Implementation Plan

1) Time Frame for Data Collection

The cost analysis will be conducted throughout the three-year RCT. The Gantt Chart describing the activities and the duration of each is shown below in **Table 2**.

Table 2 rTMS for Treatment-Resistant Major Depression Trial – Cost Analysis

Gantt Chart

Activity:	Year 1				Year 2				Year 3				Year 4				Year 5				Year 6				
	Quarter				Quarter				Quarter				Quarter				Quarter				Quarter				
	1	2	3	4	1	2	3	4	1	2	3	4	1	2	3	4	1	2	3	4	1	2	3	4	
1. Establish data collection routine at local sites for Intervention Costs																									
2. Collect cost of production data on each subject																									
3. Extract prior-year VHA data for each enrolled subject																									
4. Extract post-year VHA data for each enrolled subject																									
5. Extract Medicare data for those using extensive non-VHA services																									
6. Analyze the cost of Intervention in each Facility																									
7. Analyze the healthcare use & cost in post-intervention year																									
8. Analyze the healthcare use & cost in pre- & post-intervention years																									
9. Analyze the cost-effectiveness																									
10. Prepare manuscripts, Final Report, etc.																									

2) Project Plan and Resource Requirements for Cost Analysis

The Cost Analysis Management Plan for this trial flows from the Gantt Chart of **Table 2**. Cost analysis will start prospective data collection of primary data collection concerning the intervention's implementation as soon as each site's IRB approves the study. In both study groups, the prior year of VHA utilization and VHA expenditures will be calculated to establish the pre-enrollment healthcare costs per patient and for each group. For each participant in the trial, VHA and Medicare utilization and expenses will be tracked and summarized for 6-months and one-year following their treatment follow-up date. For some portion of the sample, we anticipate having more than one-year of follow-up experience recorded in the AAC encounter data, which will permit modeling of longer-term impacts.

The cost analysis will be conducted centrally at the Perry Point Cooperative Studies Branch. The Investigator time will include: 12.5% of two Health Economists, and 80% of an advanced Outcomes Programmer throughout the six-year RCT. **At each site, the primary data**

collection effort will require 5% of a research coordinator to collect the Intervention's Costs of Implementation. This allows for the start-up and implementation period and the manuscript and final report generation periods in addition to the four-year data collection period described above in **Table 2**.

a) Investigative Team

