Data Sources. **Table 1** summarizes constituent components of utilization and cost and their corresponding data sources. Components are divided by whether they will be used to measure costs for active rTMS only (Tx Group = Active) or for both sham and active rTMS (Tx Group = Both). Health care utilization will be determined from national VA data systems, patient responses recorded on study forms, and study case report forms (adverse events, in particular). Cost estimates will be derived from national VA data systems, published sources, and accounting values provided by VA administrators.

We will use centralized VA databases to obtain the health care services used by the trial participants. From the database of VA inpatient hospital stays, the Patient Treatment File (PTF), we will obtain the date of discharge, days of stay in each ward (bedsection), including the number of days in intensive care, and the ICD-9 diagnoses (up to 10 codes) assigned to the stay. Then, we will obtain from the outpatient care file (OPC), the date of the visit, the location of care (stop code), and ICD-9 diagnoses (up to ten) and CPT codes (up to five) assigned to describe the visit and the type of provider. All major types of outpatient care are captured, including mental health and substance abuse as well as general medical services utilization. The cost of other care (including diagnostic tests) will be obtained from detailed utilization data, which is available from centralized VA Austin databases. National VA utilization databases (PTF and OPC) lack cost estimates, but they can be merged to the Health Economics Resource Center (HERC) average cost database, and accepted methods applied.

Table 1. Resource Utilization and Associated Costs

Tx Phase/Resource Category	Tx Group	Primary Source(s) and Notes
Pre-screening for patient safety	Active	Case report forms and provider wage rates
Treatment for rTMS-related adverse medical events	Active	Adverse events reporting forms, OPC and PTF, and administrative HERC files. We will link study data on adverse events with administrative data on services utilization and costs.
rTMS device and associated physical equipment costs	Active	Equipment prices will be obtained from study investigators. Average per session expense will be imputed using straight-line depreciation plus rental cost, with per session costs distributed across the equipment's useful lifetime.

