Staff time during rTMS sessions	Active	Case report forms and provider wage rates
Staff time for planning ongoing rTMS care and for post-treatment services	Active	Provider reports
rTMS-related non-clinical administrative staff time	Active	Administrative staff reports
rTMS-related medical supplies	Active	Study investigators and administrative staff
rTMS-related electricity expense and other overhead	Active	Study investigators and administrative staff
Office space for rTMS sessions	Active	Study investigators and administrative staff. Imputed rental cost.
rTMS-related computer resource use	Active	Study investigators and administrative staff
Inpatient stays	Both	VA administrative HERC cost files
All non-rTMS outpatient visits	Both	VA administrative HERC cost files
Prescription medication	Both	DSS pharmacy extracts and Pharmacy Benefits Management (PBM) data.

Comparison of HERC & DSS Costs. Data from the VA administrative HERC average cost data files will be used to estimate most outpatient and inpatient costs.¹²⁻¹⁵ The HERC average cost data provide cost estimates; the true cost is unknown. For a second set of cost estimates, we will use the VA Decision Support System (DSS). DSS is a detailed cost allocation system that was implemented in 1997 across the VA. Although DSS is a sophisticated accounting tool that taps VA cost and utilization databases for “real time” managers’ use, its use by researchers is limited. Ongoing validation studies with DSS data show that the cost estimates need to be carefully reviewed to find administrative errors. Because DSS is not standardized nationally, we will use DSS as a secondary source of cost and utilization data in a sensitivity analysis. Recent research compared the HERC and DSS

cost estimates, and the research provides guidance on how to use DSS to test the sensitivity of the HERC data.¹⁶

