We will estimate the average cost differences between active-rTMS and usual care during the acute treatment phase and the follow-up phase. Two analyses will be conducted, one for the period extending 24-weeks post-treatment and one for the period extending 6- to 12-months post-treatment. Total average direct and indirect health care costs for all inpatient and outpatient care will be included in our estimates. Will also produce separate estimates by study phase (treatment or follow-up), in order to isolate any post-treatment cost-offset effects. We will

collect utilization and cost data from HERC, DSS Pharmacy, PBM, and National Patient Care Database (OPC and PTF) files for at least a 30-month period, starting one year prior to the date of randomization and extending one year after the end of the treatment follow-up phase. For patients randomized to sham-rTMS, we will assume that health care utilization and costs during the post-treatment phase are representative of usual health care utilization and costs for these patients. An imputation approach (described in the next paragraph) will be used to estimate their cost of usual care during the acute treatment phase.

Usual Care Costs for Patients Randomized to Sham rTMS. As noted earlier, usual daily cost values will be imputed for patients in the comparison group. Imputation is necessary because our cost analysis requires an estimate of the difference between the cost of providing rTMS intervention and the cost of providing “usual services over a similar period of potential intervention time”. This “incremental cost” cannot be estimated by the difference in average health care costs during the acute treatment phase between the active- and sham-rTMS treatment groups. The estimator for the average incremental cost of rTMS can be expressed as $E(C | T_a) - E(C | T_u)$, where C is health care cost, T_a indicates receipt of active rTMS and T_u indicates receipt of usual care. In randomized trials, estimates of the second component of this expression, $E(C | T_u)$, are normally calculated as the average cost of care in the comparison group. In this trial that approach is problematic, because this trial will not include a “usual care” group, and the sham-rTMS group will potentially get protocol-driven additional days of care as compared to the active-rTMS group, if the latter is more effective.

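### Appendix M costs every non-rTMS outpatient visit with no exclusion of trial-only encounters, and because only the active arm's acute-phase cost is observed, any that are recorded inflate the incremental cost and the ICER

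*Protocol*

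**What the plan says.** Appendix M, section D.1, Table 1 lists "All non-rTMS outpatient visits" as a cost component for both treatment groups, taken from the HERC cost files. Resources tied to rTMS itself are separate rows charged to the active group only.

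Three other statements bear on the scope:

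- Section D.3 is all-inclusive: "Total average direct and indirect health care costs for all inpatient and outpatient care will be included in our estimates".
- Section D.1 adds tests: "The cost of other care (including diagnostic tests) will be obtained from detailed utilization data". For each outpatient visit it extracts, among other items, "the date of the visit, the location of care (stop code), and ICD-9 diagnoses".
- The only stated reconciliation with study records to prevent double counting concerns dispensed medication (D.1, Pharmacy Costs).

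Section D.3 recognises trial-induced care in one place. It explains that sham acute-phase costs cannot serve as usual care partly because "the sham-rTMS group will potentially get protocol-driven additional days of care as compared to the active-rTMS group". They are replaced by each sham patient's average daily VA cost "during the 6-month period immediately preceding the date of study recruitment", multiplied by the mean length of acute treatment in the active arm. For follow-up, the sham arm's observed "costs during the post-treatment phase are representative of usual health care utilization and costs for these patients".

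Section D.4 defines the ICER as the difference in mean acute treatment cost divided by the difference in remission probability.

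**The concern.** The overview of Appendix M says the aim is the cost of rTMS to the VA at a typical site, compared with usual outpatient care. Encounters that exist only because patients are in a trial belong to neither side. The plan removes them from the sham arm's acute phase through the imputation but has no matching step for the active arm.

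The error would therefore run in one direction, against rTMS. It would enter the ICER numerator in full, as well as any cost-consequences contrast that includes the acute phase. How large it is would depend on how each site records research visits, which the analysis should not depend on.

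**Working it through.** The plan states no figure for this quantity, and section D.6 gives no power analysis, so there is nothing to reproduce. The check is an accounting of study-only visits by arm and phase.

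**Inputs**

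- Acute assessment points, *k*. Form 20 and the other rating forms schedule sessions 5, 10, 15, 20, 25 and 30. Appendix K sets 20 to 30 sessions, so *k* is 4 to 6.
- Follow-up assessment points: 6 (weeks 4, 8, 12, 16, 20 and 24). Appendix K, section 6 puts all patients in both arms into follow-up.
- Cost per study-only encounter, *c*: **assumed** $50 to $300. The protocol gives no figure.
- For scale: $5,535 per depression patient per year (Appendix M, C.2); acute phase of 4 to 11 weeks, that is 28 to 77 days (Appendix M, A); remission of 9% against 6% (Appendix G, 2008 meta-analysis). A 10-point remission gain is an added assumption.

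**Load of study-only visits if every point is recorded as a separate encounter**

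| Phase | Active | Sham | Difference |
|---|---|---|---|
| Acute | *k* × *c* (observed) | 0 (imputed from before recruitment) | *k* × *c* |
| Follow-up | 6 × *c* | 6 × *c* | 0 |

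**Shift in incremental cost**

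- Lowest: 4 × $50 = $200.
- Highest: 6 × $300 = $1,800.

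**Follow-up level, each arm**

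- 6 × $50 = $300 to 6 × $300 = $1,800, with a net difference of about zero. A small residue could arise from taper weeks, which only remitters attend.

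**Shift in ICER = *k* × *c* / remission difference**

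- At 3 points: $200 / 0.03 = $6,667 to $1,800 / 0.03 = $60,000 per remission.
- At an assumed 10 points: $200 / 0.10 = $2,000 to $1,800 / 0.10 = $18,000.

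**Scale of the imputed comparator**

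- $5,535 / 365 = $15.16 per day.
- 28 days: $425. 77 days: $1,168.
- If treatment-resistant patients cost twice this average: $849 to $2,335.

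Under these assumptions the shift could be of the same order as the usual-care cost it is compared with. The plan will use each patient's own prior costs, so these comparator figures serve only as a yardstick.

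**Do the planned checks reach it?** The usual-cost check in section D.5 compares sham-arm costs with those of similar VA patients outside the trial. That tests the comparator, not the active arm's acute cost. The alternative price indices and discount rates, the DSS cost source and the exclusion of deaths do not address it either.

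**The case against.** The strongest objection is that nothing in the protocol says study assessments create encounters in the outpatient or HERC files. A reader might infer from Table 1 that the trial's research visits and tests *are* being counted as VA care. The documents do not support that. They show only that such visits are not excluded. Several details suggest the number recorded may be small:

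- Acute ratings are keyed to treatment sessions, so some may take place within rTMS visits, which the row already leaves out. Form 16 also allows contact by telephone or mail.
- Audiometers and drug and alcohol kits are supplied centrally for the study, and the neuropsychological battery is a study form, so these need not appear as clinic or laboratory workload.
- Form 14 asks for a birth-control and pregnancy assessment every 4 weeks and then asks whether a test was done. It does not require a pregnancy test every 4 weeks.
- The HRSD after sessions 20, 25 and 30 decides continuation or taper. It is part of the regimen and not clearly a research encounter.

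A reader might also infer that follow-up visits distort the comparison by loading sham usual care. They do not, because both arms share the same schedule. Only the level is affected.

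Finally, clinic-code rules are often left to an analysis plan. The first part of the protocol and a few pages of Appendix M were also not available, so an exclusion stated there cannot be ruled out.

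These objections limit the size and certainty of the point. They do not remove it: the row and section D.3 state an all-inclusive rule, and the costing of the acute phase is asymmetric as written.

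**Conclusion.** The point holds in conditional form. Followed literally, Appendix M would count any study-only outpatient encounter or test that reaches the VA files. In the acute phase such encounters would count against the active arm only, so the incremental cost and the ICER would be biased upward.

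The size cannot be determined from the protocol. The $200 to $1,800 per active patient rests on an assumed unit cost and on every acute assessment being a separate recorded encounter. It falls to the extent that ratings happen within rTMS visits or belong to routine rTMS care, and it is zero if sites do not record study visits as encounters.

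In follow-up, the consequence is a raised cost level in both arms, including the level labelled usual care, with little effect on the difference.

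**What to change.** Amend the Table 1 row to read: *all outpatient visits except rTMS sessions and protocol-required study-only visits and tests*. State that these are identified in both arms and both phases by matching outpatient visit date and stop code, which the plan already extracts, to the dated study forms.

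Keep assessments that routine rTMS delivery would need, such as the HRSD used to decide continuation or taper, as a micro-costed row under rTMS. Report the cost difference and the ICER with dual-purpose visits included and excluded.

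The cost is one match between files that the study will hold anyway. The downside is some judgement in classifying visits that served both research and care, which the two-way reporting makes visible. If few study visits turn out to be recorded, the step changes little and documents that fact.

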It cannot be known *a priori* if rTMS therapy will increase or reduce usual VA health care costs associated with treatment-resistant depression. This innovation, rTMS, may increase costs during the acute treatment phase due to more frequent contact with outpatient providers, greater frequency of lab tests, use of an expensive rTMS medical device, and greater use of other resources. However, these extra costs could be partially or completely offset by savings from reduced likelihood of later hospitalization, reduced likelihood of receiving electroconvulsive therapy (ECT), reduced use of psychotropic medications, and/or reduced frequency of depression-related medical encounters. If rTMS therapy increases the likelihood of a full remission and/or reduces the likelihood of a recurrence, cost-offset effects will tend to accumulate over time. Because there is presently little evidence on the cost and effectiveness of rTMS in usual clinical settings, the magnitude of shorter and longer term potential cost differences between rTMS and usual care are unknown. Two hypotheses about the short-term (24-weeks post-treatment) and longer term (6- to 12-months post-treatment) cost consequences of rTMS therapy will therefore be tested:

1. Relative to usual care, total direct and indirect VA costs related to rTMS therapy for treatment-resistant depression will be less than total costs associated with usual care at 6-weeks post-treatment.
2. Relative to usual care, total direct and indirect VA costs related to rTMS therapy for treatment-resistant depression will be less than total costs associated with usual care at 6- to 12-months post-treatment.

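### The post-treatment cost comparison in Appendix M is described only as a difference in averages, and no stated between-arm estimate uses the prior-year cost calculated for both arms

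*Protocol*

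**What the plan says.** Appendix M, section B (Objectives) announces formal testing: "Two hypotheses about the short-term (24-weeks post-treatment) and longer term (6- to 12-months post-treatment) cost consequences of rTMS therapy will therefore be tested". Section D.3 (rTMS Cost Consequences) describes the estimate: "We will estimate the average cost differences between active-rTMS and usual care during the acute treatment phase and the follow-up phase". It also promises separate estimates by phase, so that any cost offset after treatment can be seen. Within the D.3 paragraph on imputing usual-care cost, the sentence that begins "The estimator for the average incremental cost of rTMS can be expressed as" gives the expected cost under active rTMS minus the expected cost under usual care. No covariate or regression model is named. D.4 describes the numerator of the cost-effectiveness ratio in the same way, as a difference in average acute treatment costs.

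The data collection reaches back before the trial. D.3 sets the window as "starting one year prior to the date of randomization and extending one year after the end of the treatment follow-up phase". F.2 says "In both study groups, the prior year of VHA utilization and VHA expenditures will be calculated", and the purpose given is "to establish the pre-enrollment healthcare costs per patient and for each group". Table 2 lists extraction of prior-year data for every enrolled subject. It also has one activity analysing use and cost in the year after the intervention and another covering the years before and after it. Neither has a method.

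The one analytic use of pre-study cost that is spelled out is the imputation in D.3. Each sham patient's average daily cost over the 6 months before recruitment is multiplied by the active arm's average acute-phase duration. D.6 gives no power for costs and allows for inconclusive results: "Whether or not these estimates reach statistical significance at conventional levels".

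**The concern.** Prior-year VA cost is the baseline value of the outcome, measured from the same national data systems in both arms. Health care costs are skewed, so a few expensive patients can dominate a mean, and prior cost is an obvious marker of who they may be. Randomization does not prevent such patients from falling unevenly between arms in a single trial. Adjusting for prior cost corrects for the part of that imbalance it predicts and narrows the interval.

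Precision matters here because two cost hypotheses are to be tested, no power is offered, and D.6 makes bounds on the cost offset a key purpose. The imputation does not help the follow-up-phase contrast: it fills in one arm's acute-phase cost, whereas in follow-up both arms have observed costs.

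**Working it through.** **Figures to reproduce.** The appendix states no sample size, standard deviation, correlation or power for costs, so there is no planned figure to reproduce. The gain can only be shown over a range of assumptions.

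**Assumptions.** ρ is the correlation between prior-year and follow-up-phase cost, taken as 0.2, 0.3, 0.5 and 0.7. The unadjusted comparison is assumed to have 80% power at two-sided 5%. Neither comes from the document.

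**Formulas.** Linear adjustment for one baseline covariate multiplies the variance of the between-arm difference by 1 − ρ². The equivalent increase in sample size is 1/(1 − ρ²). Power after adjustment is Φ((1.960 + 0.842)/√(1 − ρ²) − 1.960).

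| ρ | 1 − ρ² | fall in variance | √(1 − ρ²) | equivalent sample size | power, from 80% |
|---|---|---|---|---|---|
| 0.2 | 0.96 | 4% | 0.980 | ×1.04 | Φ(0.90) = 82% |
| 0.3 | 0.91 | 9% | 0.954 | ×1.10 | Φ(0.98) = 84% |
| 0.5 | 0.75 | 25% | 0.866 | ×1.33 | Φ(1.27) = 90% |
| 0.7 | 0.51 | 49% | 0.714 | ×1.96 | Φ(1.96) = 98% |

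**Does the formula survive skewed costs?** It was checked by simulating correlated lognormal costs, with log-scale standard deviation 1.0 or 1.3 and 80 or 180 per arm, all assumed. The ratio of adjusted to unadjusted variance was 0.91 to 0.96 at correlations of about 0.2 to 0.3, 0.72 to 0.79 at about 0.4 to 0.5, and 0.46 to 0.52 at about 0.65 to 0.7. This is close to 1 − ρ², and in most settings a little lower.

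**What the document says about skew.** Under Current VHA Target Population, 9,676 of 130,193 patients (7.4%, printed as 7%) cost more than $75,000 a year. The mean is $4,152,226,250 / 130,193 = $31,893. That group was hospitalised at least once in the year and includes dementia and brain injury. The trial-eligible pool described in the next section averages $161.3 million / 21,443 = $7,522, under a quarter of that mean, and no high-cost share is given for it. The first pair of figures illustrates skew and does not describe trial participants.

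**Which contrast gains.** Section B's hypotheses concern total costs. A total that covers the acute phase contains, for the sham arm, an amount that is itself a multiple of that patient's own pre-study cost. It therefore depends on the covariate by construction in one arm only, and 1 − ρ² does not carry over. The table applies to the follow-up-phase contrast.

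**The case against.** The strongest reply is that the appendix is silent on adjustment and does not exclude it. An average cost difference is a quantity, and a covariate-adjusted model estimates the same quantity. Covariates are often left to a statistical analysis plan, which is not available here, nor is the first part of the protocol. Table 2's pre/post activity might be such an adjusted analysis.

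This stands in part. A reader might infer that the protocol fixes an unadjusted comparison and discards the baseline data. The text does not support that: no sentence rules out adjustment, and the pre/post activity is undefined either way. But Appendix M is itself a detailed economic plan. It writes out the imputation, the cost-effectiveness ratio, bootstrap confidence regions, discount rates and propensity-score predictors. At that level of detail, giving the between-arm estimate only as a difference in averages, and the prior-year cost only a descriptive purpose, is a fair place to name the better method.

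A reader might also infer bias. There is none: the unadjusted difference is unbiased over randomizations, and its interval already allows for chance imbalance. Nor should the 7% share and the mean of about $31,900 be read as the trial's own cost distribution, or the power gains as applying to section B's hypotheses on total cost.

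Finally, the gain may be small. At ρ = 0.2 it is under 2 percentage points of power.

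**Conclusion.** The point holds as an inexpensive gain in efficiency, with no threat to validity. Prior-year VA cost is to be calculated for both arms, and no stated between-arm estimate uses it. Adjusting the follow-up-phase difference would reduce its variance by between 4% and 49% over the assumed range of ρ, and would remove the part of any chance imbalance that prior cost predicts. The size rests on an unknown correlation and an assumed starting power. No gain is claimed for totals that include the imputed acute-phase cost.

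**What to change.** Add to Appendix M, D.3:

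- Estimate the follow-up-phase cost differences, including the post-treatment part of the 24-week and the 6- to 12-month windows, by regressing cost on arm with the participant's VA cost in the year before randomization as covariate.
- Use ANCOVA on dollars with robust or bootstrap standard errors, or a gamma GLM with recycled predictions, so that the result remains a difference in mean dollars. Choose one in advance.
- Keep the unadjusted difference as a supporting result.
- Where a total includes the sham arm's imputed acute-phase cost, report the adjusted follow-up contrast separately and claim no precision gain for the total.
- State whether the pre/post activity in Table 2 is this analysis or something else.

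The cost is a few sentences. Extraction of the data is already planned for every participant, so no patients, visits or staff time at sites are added.
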